**In Vivo Evaluation of Antibacterial Toothpaste Efficiency and Patients' Satisfaction:
a Double-blind Randomised Controlled Trial**

NCT05569850

November, 20th 2024

Study Protocol

This was a single-site, double-blind RCT that was conducted in the Dental Clinic of Bologna University (DIBINEM), Bologna, Italy in the period from November 2022 until July 2023. Before initiating the trial, the study protocol was reviewed and approved by the University Ethics Committee (793/2022/SPER/AUSLBO). The trial was in accordance with Helsinki Declaration of Human Rights [21] and followed the CONSORT statement. The tested dentifrices included a newly introduced ZCT-, HAP- and KCit- 1450 ppm sodium monofluorophosphate containing (Experimental group; Mentadent PROTECT+ Carie, Mentadent, Unilever, Milan, Italy) and 1450 ppm NaF containing (Control group; AZ Multi-Protezione Scudo Protettivo Famiglia) toothpastes.

Sample size, recruitment and eligibility criteria

The number of patients was determined based on the power analysis performed using data from a previously published study in order to assure a power of 80% for finding the statistically significant differences given the standard value of type I errors (0.05). Based on the outcomes of the power calculation (effect size $f=0.2291667$, at the level of α 0.05, and $1-\beta$ prob 0.80), the determined sample size was 92 patients. Considering the probability of loss to follow-up 10% of the minimum size per group was added, leading to the final sample size of 100 patients.

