Potential patients were recruited through local advertisement or on-site, during routine dental check-ups. Study details were explained to the potential participants and only those who voluntarily signed the informed consent were scheduled for the first visit. During the screening phase, one dentist evaluated the eligibility of the patients in the study based on the following inclusion criteria: male and female patients aged 18-50 with minimum of 20 natural teeth in stable occlusion and good oral hygiene level (bleeding on probing not exceeding 20%, no advanced periodontal disease, absence of active caries lesions, pulpitis), patients with good general health (no systemic diseases reported in the medical anamnesis), and subjects with good language comprehension. Exclusion criteria were tooth anomalies (i.e. amelogenesis imperfecta, dentinogenesis imperfecta etc.), intrinsic stain (i.e. fluorosis, molar incisors hypomineralization [MIH]), active caries lesions, advanced periodontal disease, smokers, presence of orthodontic devices, use of antibiotics in the last 3 months, use of antibacterial mouthrinses in the last 3 months, reported allergies, drug and alcohol addiction.

Study procedures

One week before the beginning of the trial, all patients received sub- and supra-gingival full-mouth prophylaxis. At the same appointment, patients were given detailed oral hygiene instructions by the dental hygienist and a brief explanatory video was shared via

messaging applications (i.e., WhatsApp) to serve as a reminder for good habits consulting during the study period. The patients were scheduled to come back after 7 days (baseline visit) and were asked not to brush or eat at least 5 hours before the appointment.

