During the baseline visit, all patients completed a custom-made questionnaire (supplementary file) containing questions regarding dental sensitivity ("self-reported" sensitivity), their perception of tooth color and overall perception of the toothpaste they were using at the time. Subsequently, they were asked to collect 2 ml of unstimulated saliva in sterile tubes (Greiner centrifuge tube, Sigma-Aldrich, St Louis, MO, USA). Saliva was immediately processed for microbiological analysis as thereafter described. Upon saliva collection, a sensitivity test was conducted by applying a tactile and air-stimulus (duration: 2 s, distance from the tooth surface: 1 cm) test to all teeth of the four quadrants. The subjects' response was recorded on a 4-point Schiff Sensitivity Scale [25] and visual-analogue scale, respectively. Additionally, plaque index (Modified Quigley and Hein) was scored on a 6 point scale at 3 buccal and 3 lingual sites per tooth after it had been disclosed with a disclosing agent (Biofilm Disclosure, EMS Dental, Nyon, Switzerland); gingival index according to Löe-Silness was also recorded, as well as bleeding on probing index. Patients' tooth color was determined under daily light using the Vita classical shade guide. Finally, at the end of the baseline visit, the participants were provided with the same soft-bristled toothbrush (Mentadent P, Mentadent, Unilever) and randomly assigned into one of the two groups (n=50) according to the dentifrice used. An online software (<https://www.sealedenvelope.com>) was utilized for randomization purposes by a staff member unaware of the study protocol. In order to enable complete blinding of the participants and dental examiner to the group assignment, the two dentifrices were distributed in identical plain white tubes provided with only letters A or B, with no other visible marks. The patient's code and dentifrice assigned (A or B) were documented in the chart for later reference. From the baseline visit, the subjects had to restrain from using any other products or means of oral hygiene except those provided and were invited to follow the domiciliary oral hygiene instructions as previously described. In case of any adverse events were to occur, the subjects were advised to discontinue the use of the toothpaste and were withdrawn from the study. The 4 weeks follow-up visit was fixed (recall).

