After 4 weeks (recall), the patients returned to the study site for a final visit after having abstained from brushing or eating at least 5 hours before the visit. During this visit, the patients were asked to fill in the questionnaire (supplementary file), while the saliva collection and all clinical procedures described above were repeated by the same dentist.

Microbiological procedures

The saliva collected during the baseline and recall visits was processed for microbiological analysis within 3 hours of sample acquisition. Briefly, 0.1 ml of saliva was diluted in 9.9 ml of sterile phosphate-buffered saline solution until 10^{-8} was reached. Subsequently, the diluted samples were dispersed on Mitis Salivarius Selective Agar (MSB, Microbiol Diagnostici, UTA, CA, Italy) and the plates were incubated at 37°C for the next 48-72h. The bacterial colonies were identified by morphology and counted by one trained investigator, blinded to the groups. *S. mutans* colonies (CFU) were multiplied by their respective dilution ratio to calculate the number of colonies per one milliliter

(CFU/mL) of each subject's saliva sample. In order to perform statistical analysis, a base-10 logarithm transformation was applied to the calculated CFU/ml values.

Statistical analysis

After checking the normality (Kolmogorov-Smirnov) and the homoscedasticity (modified Levene's test) of the data, the Two Way Repeated Measures ANOVA (One Factor Repetition) followed by Bonferroni post-hoc were run to investigate the effect of the tested dentifrices on salivary counts of *S. mutans*, as well as plaque and gingival indexes. Since the data retrieved from questionnaires were not normally distributed (Kolmogorov-Smirnov, $p<0.05$), the non-parametric Mann-Whitney U-test was run. All analyses were performed by a statistician blinded to the groups using SigmaPlot 14.0 (Systat Software, Chicago, IL, USA). In all tests, the significance level was set at $\alpha=0.05$.

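### The repeated-measures ANOVA uses the pre-randomisation baseline as an outcome and names no dentifrice test; one baseline-adjusted ANCOVA per outcome would give a single test, with a precision gain that depends on the unstated baseline-recall correlation

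*Combined protocol and SAP*

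**What the plan says.** In the combined protocol and SAP, Study procedures describes saliva collection and then the plaque and gingival scoring. Only after these, "at the end of the baseline visit, the participants were provided with the same soft-bristled toothbrush (Mentadent P, Mentadent, Unilever) and randomly assigned" to a dentifrice. At four weeks "the saliva collection and all clinical procedures described above were repeated by the same dentist". Each outcome therefore has one value before randomisation and one after.

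Under Statistical analysis, "the Two Way Repeated Measures ANOVA (One Factor Repetition) followed by Bonferroni post-hoc were run to investigate the effect of the tested dentifrices" for three outcomes: S. mutans (log10 CFU/mL), plaque index and gingival index. The repeated factor is not named, but baseline and recall are the only two measurement occasions. The section does not say whether the dentifrice effect is the arm main effect, the arm-by-visit interaction or a post-hoc contrast at recall. It lists no post-hoc pairs and mentions no baseline adjustment. It does say that "All analyses were performed by a statistician blinded to the groups".

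The sample-size section cites "the power analysis performed using data from a previously published study" and gives f=0.2291667, alpha 0.05 and power 0.80, concluding that "the determined sample size was 92 patients". It does not state the outcome, the test, the number of visits or the baseline-recall correlation.

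**The concern.** A value measured before randomisation cannot respond to treatment. In a two-arm trial with one follow-up visit it serves best as a covariate. Entering it as an outcome level produces several terms that could each be read as the dentifrice effect:

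- **Arm main effect.** The expected baseline difference is zero, so this term estimates (0 + recall difference)/2, half the quantity of interest.
- **Arm-by-visit interaction.** With two visits this is the comparison of change scores. It is valid and unbiased.
- **Recall contrast.** Also valid and unbiased, but it ignores baseline.

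Because no term is named, a reader cannot tell which p-value answers the trial question. If the main effect is read, the reported difference is half the recall difference. If a valid term is read, the estimate is unbiased but usually less precise than the data already collected allow. If the deciding term were picked by its p-value, the error rate would exceed 5%. The documents do not show that this happened. Blinding the statistician limits choice by direction, but not choice by p-value.

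**Working it through.** **Inputs.** From the documents: 92 evaluable patients, taken as 46 per arm; alpha 0.05; f=0.2291667; two visits. Assumed: two-sided tests, equal SDs at both visits, and r from 0 to 0.8. The documents do not give r. It may be low, because "One week before the beginning of the trial, all patients received sub- and supra-gingival full-mouth prophylaxis".

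**The plan's own figure.** For two groups, f² = 0.0525174.

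- Single-visit comparison: noncentrality N·f². This needs N=152 for 80% power (152 × 0.0525174 = 7.98). At N=92 power is 58.5%.
- Arm effect averaged over two visits: noncentrality N·f²·2/(1+r). At r=0.2 this is 92 × 0.0525174 × 2/1.2 = 8.05, giving 80.2% power at exactly 92.
- Change-score test with a recall difference of 2f: noncentrality N·f²/[2(1−r)]. At r=0.7 this is 92 × 0.0525174/0.6 = 8.05, again 80.2%.

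So 92 is not shown to be wrong, but it does not reveal which test was intended. The diluted main effect is one live candidate.

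**Variances.** Per patient, in units of the SD squared, for the recall difference:

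- interaction: 2(1−r)
- recall contrast: 1
- ANCOVA: 1−r²
- main effect: (1+r)/2 for half the difference, hence 2(1+r) after doubling

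The interaction and the recall contrast are equal when 2(1−r)=1, that is r=0.5. Below that the recall contrast is the more precise, above it the interaction. In large samples the ANCOVA variance is (1+r)/2 times that of the interaction and 1−r² times that of the recall contrast.

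**Precision.** The 95% CI half-width in SD units is t × √(2/46) × √variance, with √(2/46)=0.2085 and t=1.987. The ANCOVA variance is inflated by 1+1/88 for the estimated slope. These figures do not depend on f.

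| r | Interaction | Recall contrast | ANCOVA | Main effect, doubled | ANCOVA against better valid term |
|---|---|---|---|---|---|
| 0 | 0.59 | 0.41 | 0.42 | 0.59 | 0.6% wider |
| 0.2 | 0.52 | 0.41 | 0.41 | 0.64 | 1.5% narrower |
| 0.5 | 0.41 | 0.41 | 0.36 | 0.72 | 13% narrower |
| 0.7 | 0.32 | 0.41 | 0.30 | 0.76 | 7% narrower |
| 0.8 | 0.26 | 0.41 | 0.25 | 0.79 | 5% narrower |

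Against the other valid term, ANCOVA is 29% narrower at r=0 (interaction) and 40% narrower at r=0.8 (recall contrast). After the slope cost, it beats the recall contrast when r exceeds about 0.11 and the interaction when r is below about 0.98.

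**Power (%) at 46 per arm.** This depends on what f means. Reading 1 takes the recall difference as 2f=0.458 SD. Reading 2 takes f as the arm effect averaged over both visits, so the recall difference is 4f=0.917 SD.

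| r | Main effect (1 / 2) | Interaction (1 / 2) | Recall contrast (1 / 2) | ANCOVA (1 / 2) |
|---|---|---|---|---|
| 0 | 33.7 / 86.8 | 33.7 / 86.8 | 58.5 / 99.2 | 58.5 / 99.2 |
| 0.2 | 28.9 / 80.2 | 40.5 / 93.0 | 58.5 / 99.2 | 60.2 / 99.3 |
| 0.5 | 24.1 / 70.9 | 58.5 / 99.2 | 58.5 / 99.2 | 70.9 / 99.9 |
| 0.7 | 21.8 / 65.5 | 80.2 / 100 | 58.5 / 99.2 | 86.1 / 100 |
| 0.8 | 20.9 / 63.0 | 93.0 / 100 | 58.5 / 99.2 | 95.2 / 100 |

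The ANCOVA column omits the slope inflation. Simulation with the slope estimated gives 58.3, 59.6, 70.4, 85.7 and 95.0% under Reading 1, within 0.6 points.

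**Error rate with identical pastes (100,000 simulated trials per r).** Each single test holds 4.9–5.1%. Free choice among all three terms gives 10.9–11.5% per outcome. Free choice between the interaction and the recall contrast gives 8.2–9.5%, or 6.3–7.2% if the recall contrast is tested at 0.025 (Bonferroni over an assumed two pairs).

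**The case against.** The strongest reply is that nothing here is biased. The interaction is a standard dentifrice test in this model and already uses each patient's baseline through the change score. What remains is an unnamed term and an efficiency preference. That is right about validity, and the point claims no bias in the valid terms.

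The gain over the better valid term is modest, and close to nothing at low r, which prophylaxis makes plausible. That also stands. But knowing which valid term is better requires r, and the plan gives neither r nor a choice.

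The error-rate figures are an upper scenario. The plan's Bonferroni step lowers the two-term figure, and if post-hoc tests are read only after a significant interaction, that pair cannot exceed 5%. The plan does not state that gatekeeping or list the pairs. The three-term figure stays near 10% even with the recall contrast at 0.025.

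The low power figures for the main effect need Reading 1. Under Reading 2 the valid terms lose little, and the precision table is the safer basis.

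Finally, the trial ran "in the period from November 2022 until July 2023", so an ANCOVA now is post hoc and adds one more candidate p-value. It cannot restore prespecification and must be labelled accordingly.

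**Conclusion.** The concern holds and should be fixed. Baseline precedes randomisation, is modelled as an outcome, and no term is identified as the dentifrice test. The main effect would report half the recall difference. The two valid terms are unbiased, but choosing well between them needs a correlation the plan does not give.

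ANCOVA removes that choice. Its interval ranges from 0.6% wider to 13% narrower than the better valid term at the r values shown, and is up to 40% narrower than the other. These figures assume 46 per arm and equal SDs at the two visits, and that visit is the repeated factor, which is inferred. The size of any power loss also depends on what f represents, so it cannot be fixed from the documents. Inflation of the error rate is possible but not shown to have occurred.

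**What to change.** For log10 S. mutans, plaque index and gingival index, report one ANCOVA each: recall value on dentifrice group plus the patient's own baseline value, giving the adjusted between-group difference with its 95% CI. Label it a reanalysis, and report the originally run ANOVA alongside it.

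If the repeated-measures ANOVA is kept as the main analysis, state that its dentifrice test is the arm-by-visit interaction and not the arm main effect, list the Bonferroni pairs, and treat within-arm changes as descriptive. The price is that below r=0.5 the interaction is the less precise of the two valid terms, which is a reason to prefer ANCOVA.

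The cost is wording in the Statistical analysis section and one rerun on existing data, with no added patients, visits or measurements. Statistically it costs one degree of freedom, about 1% in variance (1/88), which outweighs the gain only if r is below about 0.11. The change gives one test per outcome and leaves multiplicity across the three outcomes as a separate matter.

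### The sensitivity comparison makes no stated use of the baseline answer, so patients with nothing to improve dilute it and a null result would say little

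*Combined protocol and SAP*

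**What the plan says.** - **Who enters** (Sample size, recruitment and eligibility criteria). The inclusion list asks for "male and female patients aged 18-50 with minimum of 20 natural teeth in stable occlusion and good oral hygiene level", along with good general health and language comprehension. Neither the inclusion nor the exclusion list mentions tooth sensitivity.
- **Who is asked** (Study procedures). At the baseline visit "all patients completed a custom-made questionnaire (supplementary file) containing questions regarding dental sensitivity", among other topics. Randomisation comes at the end of that visit. The questionnaire is filled in again at the 4-week recall.
- **How it is analysed** (Statistical analysis). The sentence on the questionnaire begins "Since the data retrieved from questionnaires were not normally distributed" and names a Mann-Whitney U test. It specifies no analysis subset and no use of the baseline answer, and does not say whether recall scores or changes are compared.
- **Other sensitivity data.** Tactile and air-stimulus responses (Schiff scale and visual-analogue scale) are recorded on all teeth, but no analysis is named for them. The Mann-Whitney test is therefore the only stated analysis that reaches sensitivity.
- **What is not given.** The response scale, the expected share of sensitive patients, and the expected effect and SD for sensitivity do not appear. The questionnaire itself is in a supplementary file that is not part of the document.

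**The concern.** The entry criteria favour healthy, well-kept mouths, so some participants, perhaps many, may have no sensitivity at baseline. Such a patient sits at the bottom of the scale whichever toothpaste is used. On recall scores these patients form one large block of ties. The test then depends heavily on how many sensitive patients chance placed in each arm, and only weakly on what the toothpaste did for them.

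Two things are at stake. First, the whole-arm average shrinks any benefit in proportion to the share of patients who could not benefit. Second, power falls, so a non-significant result could be read as no effect on sensitivity when the comparison had little chance of showing one.

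**Working it through.** **The plan's own figure.** The document says "the determined sample size was 92 patients", from f = 0.2291667, alpha 0.05 and power 0.80, without naming the outcome. A plain two-group ANOVA with these inputs needs 152. A repeated-measures between-group test with two visits and correlation ρ has noncentrality N·f²·2/(1+ρ). At N = 92 and ρ = 0.2 this is 92 × 0.0525 × 2/1.2 = 8.05, which gives 80% power. So 92 can be reached, but only with an unstated input such as ρ = 0.2. It can be neither confirmed nor refuted, and nothing ties it to sensitivity. It is used here only for the arm size: 92/2 = 46.

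**Assumptions (not in the documents).** A 0–10 rating. Sensitive control patients have mean 4 and SD 2 at recall. The true benefit is 1.5 points, in sensitive patients only. The baseline–recall correlation is 0.5. New sensitivity appears in 5% of the others. Tests are two-sided at 0.05.

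**Dilution of the estimate.** The whole-arm benefit is roughly the share sensitive times the benefit among them. The floor at zero reduces the 1.5 points to about 1.39 observed among sensitive patients. At a 30% share, 0.30 × 1.39 = 0.42, close to the simulated whole-arm value of 0.41.

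**Power by simulation, 46 per arm.**

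| Analysis | 20% sensitive | 30% | 50% |
|---|---|---|---|
| Whole arm, recall scores, Mann-Whitney | 7% | 10% | 22% |
| Whole arm, change scores, Mann-Whitney | 20% | 32% | 56% |
| Whole arm, baseline-adjusted (ANCOVA) | 25% | 41% | 70% |
| Baseline-sensitive subset, recall scores, Mann-Whitney | 26% | 41% | 65% |
| Baseline-sensitive subset, baseline-adjusted | – | 53% | – |

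Type I error was 4.7–5.3% for every method. The figures move with details that also have to be assumed. For example, whole-arm change-score power at 30% was 33% with baseline mean 4 and 22% with baseline mean 5.

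**Second set of assumptions.** 50 per arm, sensitive mean 5, SD 2, correlation 0.5, effect 0.8 SD, all others at zero at both visits.

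| Share sensitive | Whole arm, recall | Whole arm, change | Subset, change |
|---|---|---|---|
| 30% | 0.08 | 0.44 | 0.53 |
| 50% | 0.21 | 0.69 | 0.76 |
| 60% | 0.33 | 0.77 | 0.83 |
| 100% | 0.97 | 0.97 | 0.96 |

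The share below which whole-arm power falls under 50% is about 70% on recall scores and about 35% on change scores. At an effect of 1.0 SD these become about 61% and 26%.

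**What restriction can and cannot do.** Sensitive patients needed per arm for 80% power are n = 2(1.96 + 0.84)²/d² = 15.7/d². That is 63, 25 and 16 for d = 0.5, 0.8 and 1.0. Dividing by 0.955 for the Mann-Whitney test gives about 66, 26 and 17. With 50 per arm, 26 means 26/50 = 52% sensitive and 17 means 34%. At d = 0.5 the arm is too small even if everyone is sensitive.

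**The case against.** **Missing the effect is not established.** A reader might infer that a real desensitising effect would usually be missed. That needs the share sensitive, the effect among them and the form of the comparison, and the documents give none of these. On change scores with half the patients sensitive and an effect of 0.8 SD, whole-arm power is 0.69, so the effect would usually be found. This objection stands.

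**Much of the loss is the unused baseline.** A reader might infer that the problem is only who is in the comparison and that baseline adjustment would not help. The figures say otherwise. At 30% sensitive, adjusting while keeping everyone raises power from 10% to 41%, the same as restricting without adjusting. Doing both adds 53 − 41 = 12 points. If the toothpaste also prevents new sensitivity, the adjusted whole-arm analysis can do better than the unadjusted subset. This stands too, and it shapes the fix.

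**The whole-arm effect is a legitimate target.** The title is about antibacterial efficiency and satisfaction. The outcomes named for the ANOVA are *S. mutans*, plaque and gingival indexes, and no desensitising hypothesis is stated. Chance imbalance in sensitive patients is noise, not bias, as the type I error shows. This is a reason to keep the whole-arm result and to rank the point as an improvement, not an error that invalidates the plan.

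**The comparison across whole arms is inferred.** The document does not state it. It is the natural reading, because nothing restricts the set, but the questionnaire file might say more.

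**Conclusion.** The point holds in a limited form. The document has no sensitivity entry criterion and puts the sensitivity questions to everyone. It describes an analysis without a baseline-sensitive subset, baseline adjustment, or a choice between recall and change. Patients with no baseline sensitivity dilute that comparison, so a null result on self-reported sensitivity would be uninformative unless most patients were sensitive or the effect was large.

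The direction follows from the design. The size rests wholly on assumed prevalence, scale and effect: in the example with 30% sensitive, power runs from about 10% to 53% depending on the analysis. The documents do not support saying that an effect would usually be missed, or that restricting the analysis would by itself give adequate power. This is worth correcting, but it does not touch the *S. mutans*, plaque or gingival results.

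**What to change.** Use the baseline answer in the sensitivity analysis:

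1. State whether the Mann-Whitney test was applied to recall or change scores.
2. Report the number and percentage sensitive at baseline in each arm, with the questionnaire rule that defines sensitive.
3. Add a baseline-adjusted between-arm comparison at 4 weeks, with a confidence interval, among participants who reported sensitivity at the baseline visit. That answer precedes randomisation, so the restriction does not bias the arms.
4. Report new sensitivity at recall separately in the remaining participants.
5. Keep a baseline-adjusted whole-arm result alongside. Leave all randomised participants in the analyses of *S. mutans*, plaque, gingival index and satisfaction.

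**Cost.** Wording and re-analysis of data already collected. The subset comparison has fewer patients and applies only to sensitive patients. It does not restore 80% power if few are sensitive. The opening of the Study Protocol dates the trial November 2022 to July 2023, and the Statistical analysis section already reports a normality result, so the added comparison must be labelled post hoc. For the same reason, changing the randomisation is no longer an option.

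### Sensitivity and tooth-colour items that match at both visits are tested without the baseline answer: a valid analysis that gives up some precision

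*Combined protocol and SAP*

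**What the plan says.** Study procedures, baseline visit: "all patients completed a custom-made questionnaire (supplementary file) containing questions regarding dental sensitivity", together with questions on perceived tooth colour and on "overall perception of the toothpaste they were using at the time". Allocation follows at the end of the same visit, when patients were "randomly assigned into one of the two groups (n=50) according to the dentifrice used". The baseline answers therefore precede randomisation.

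Study procedures, 4-week recall: "the patients were asked to fill in the questionnaire (supplementary file", with the same file reference as at baseline. That file is not among the documents, so which items are repeated in identical form cannot be checked.

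Statistical analysis: *S. mutans* counts and the plaque and gingival indexes get a two-way repeated-measures ANOVA, which uses both visits. For questionnaire data the section cites non-normality and says that "the non-parametric Mann-Whitney U-test was run". It gives no visit, change score or baseline covariate. The test compares two independent samples, so dentifrice A against B is the natural reading. Whether it was applied to recall answers or to change from baseline is left open.

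**The concern.** A patient's answer at 4 weeks is likely to resemble that patient's answer before randomisation. Where it does, part of the spread between patients at recall can be explained by a value already collected, and removing it sharpens the comparison of arms. A Mann-Whitney test at recall ignores that value. A Mann-Whitney test on change uses it with a fixed weight that is usually not the best one. Non-normality, the only reason given for choosing the test, does not require setting baseline aside, because rank ANCOVA and proportional-odds models both handle such data.

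At stake is the chance of detecting a real difference in self-reported sensitivity or perceived colour with 50 patients per arm. Patient satisfaction is in the trial's title, so these outcomes are not incidental.

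**Working it through.** **Plan's own figure.** There is none for this point. The calculation leading to 92 patients (100 after the dropout allowance) names no questionnaire outcome, and nothing below depends on it.

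**Inputs from the documents.** 50 per arm; alpha 0.05; baseline answers given before randomisation; one recall at 4 weeks.

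**Assumed inputs, because the documents give none.** A latent shift of 0.5 SD in either direction, latent baseline-recall correlation r of 0.3, 0.5 or 0.7, and three answer scales:
- five categories of 20% each;
- four categories at 70/15/10/5% (floor-heavy);
- yes/no with 30% yes.

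The floor-heavy scale is an inference from the eligibility criteria, which require "absence of active caries lesions, pulpitis". No prevalence of sensitivity is given.

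**Theory.** With equal variance at both visits, the variance of the arm contrast relative to recall only is:
- recall only: 1
- change: 2(1 − r)
- baseline-adjusted: 1 − r²

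At r = 0.3/0.5/0.7 the adjusted variance is 0.91/0.75/0.51 and the change variance 1.40/1.00/0.60. Adjusted relative to change is (1 + r)/2 = 0.65/0.75/0.85. Change beats recall only when r exceeds 0.5.

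**Effect of coarse scales.** Cutting a latent scale into categories lowers the correlation actually observed. Variance reduction is the squared observed rank correlation, and the equivalent number of unadjusted patients is 100/(1 − ρ²). Order: r = 0.3/0.5/0.7.

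| Item | Observed ρ | Variance reduction | 100 adjusted patients are worth |
|---|---|---|---|
| Five even categories | 0.269/0.452/0.645 | 7/20/42% | 108/126/171 |
| Floor-heavy | 0.202/0.355/0.532 | 4/13/28% | 104/114/139 |
| Yes/no | 0.182/0.319/0.481 | 3/10/23% | 103/111/130 |

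**Simulated power.** 4,000 replicates per cell, Monte Carlo SE about 0.008, 50 per arm. Rank ANCOVA regresses the rank at recall on arm and baseline rank. Order: r = 0.3/0.5/0.7.

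| Item, shift | Mann-Whitney, recall | Mann-Whitney, change | Rank ANCOVA |
|---|---|---|---|
| Five even, −0.5 | 0.647/0.633/0.650 | 0.461/0.574/0.762 | 0.677/0.739/0.858 |
| Five even, +0.5 | 0.639/0.640/0.637 | 0.468/0.560/0.760 | 0.667/0.731/0.856 |
| Floor-heavy, −0.5 | 0.432/0.448/0.442 | 0.238/0.290/0.387 | 0.444/0.492/0.556 |
| Floor-heavy, +0.5 | 0.556/0.552/0.544 | 0.416/0.510/0.650 | 0.576/0.613/0.698 |
| Yes/no, −0.5 | 0.416/0.416/0.450 | 0.246/0.284/0.361 | 0.427/0.454/0.523 |
| Yes/no, +0.5 | 0.505/0.520/0.519 | 0.349/0.405/0.499 | 0.508/0.546/0.611 |

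**Gain of rank ANCOVA over recall**, in power points over both directions:
- five even categories: 3 / 9–11 / 21–22
- floor-heavy: 1–2 / 4–6 / 11–15
- yes/no: 0–1 / 3–4 / 7–9

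**Gain over change**, across the three correlations: 10–22, 5–21 and 11–18 points. Rank ANCOVA is ahead in every cell of the table.

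**Limits of the range.** These come from a separate set of runs with 46 per arm, a 0.62 SD shift and five-point items. At r = 0 there was no gain over recall (0.800 v 0.796 on a symmetric item; 0.768 v 0.768 with about 55% at the floor). At r = 0.85 on the floor item, change and rank ANCOVA were level (0.982 v 0.981).

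**Type I error.** 0.043–0.057 for all three tests in the 4,000-replicate runs.

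**Model-based alternative.** A proportional-odds likelihood-ratio test with baseline, shift −0.5 only, had power:
- 0.69/0.75/0.87 on five categories (1,500 replicates)
- 0.48/0.52/0.58 on the floor-heavy item (600 replicates)
- 0.43/0.46/0.49 on yes/no (600 replicates)

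For yes/no that is a gain of about 1/4/4 points over recall, against 1/4/7 for rank ANCOVA at the same shift. With 600 replicates the SE is about 0.02, so this difference may be noise. The model's type I error was 0.038–0.068 (SE 0.006–0.010).

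**The case against.** The strongest reply is that Mann-Whitney is a standard, valid choice for outcomes that no section calls primary, and that no actual loss is shown for any item, because matching, scale and correlation are all unknown. This stands, and it makes the point minor and conditional. The gain may be close to nil, and prophylaxis and hygiene instruction one week before baseline could weaken the correlation (an inference, not a documented fact).

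Timing also counts. The trial ran "in the period from November 2022 until July 2023" and the test is reported as already done, so an adjusted analysis now is post hoc and cannot carry a confirmatory claim.

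A reader might infer four stronger things, none of which the documents or the calculations support:
- **That the questionnaire results are biased or the test invalid.** Randomisation protects both contrasts, and type I error held.
- **That an analysis on change would always lose more than one at recall.** It does at low or moderate correlation. At r = 0.7 it loses less on the five-category item (10 v 21–22 points) and on the floor-heavy item with an upward shift (5 v 15).
- **That gains near 20 points, or 171 equivalent patients, should be expected.** Those need the highest correlation tried and the evenly spread scale.
- **That toothpaste perception is affected.** Its baseline item concerns the product used before the trial, so it is not a baseline for the study dentifrice.

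**Conclusion.** The point holds as a minor, conditional loss of precision. The baseline answers exist, precede randomisation and are not used by the stated test unless it was run on change. For matching sensitivity or colour items, rank ANCOVA was more powerful than either reading of Mann-Whitney at every correlation from 0.3 to 0.7 that was tried. Over Mann-Whitney at recall the gain runs from essentially nothing to about 22 points. The size rests on the assumed 0.5 SD shift, answer scales and correlations, and on items being identical at both visits, which only the supplementary questionnaire can confirm. The choice between recall and change also matters: on the five-category item with shift −0.5 at r = 0.3 it moves power from 0.647 to 0.461.

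**What to change.** 1. Check the supplementary questionnaire for sensitivity and colour items asked in the same form at both visits.
2. For those items, compare arms at recall adjusted for the patient's own baseline answer. Use rank ANCOVA, to which the gains above refer, or a proportional-odds model (logistic for yes/no) with the adjusted odds ratio and 95% CI. For yes/no items the logistic gain may be smaller.
3. Keep Mann-Whitney at recall for toothpaste perception and for items without a matching baseline, and state the contrast used for every item.
4. Label the adjusted analysis post hoc, show it beside the Mann-Whitney result for every matching item, and do not choose between them by p-value.

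**Cost.** No new data: one model per matching item and a sentence on the contrast. The downsides are added analytic flexibility, possibly other software ("All analyses were performed by a statistician blinded to the groups using SigmaPlot 14.0"), and an odds ratio that is conditional on baseline and so is not the quantity Mann-Whitney tests.
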